5.2.2 Secondary and Tertiary Outcome Variables (if applicable)

Secondary outcomes will be measures of clinical effectiveness—BP control and adherence to antihypertensive medications at the pre-intervention (baseline) and post-intervention (12 month) periods.

BP control, the major secondary outcome, will be defined as SBP <140 and DBP <90 mmHg. BP control will be assessed using the mean of the last two measurements recorded in the EHR during each of the pre-intervention and post-intervention study periods (baseline and 12 months). BP readings will be extracted from patients' EHR by trained RAs. We will use the last two recorded measures to reduce variability associated with multiple BP measurements being taken by different clinic staff. We will also examine the proportion of patients with BP control <130/80 mmHg in exploratory analyses to provide preliminary data on BP control rates of hypertensive patients when considering the new guidelines. We will also explore mean change in systolic and diastolic BP based on the mean of the last two recorded BP readings in the EHR during the pre- and post-intervention periods.

Medication adherence will be assessed via pharmacy refills obtained from prescription orders in the clinic EHR using the proportion of days covered (PDC) metric. The PDC is calculated as the total number of days covered by the medication divided by the number of days between the first fill of the medication in the study period and the end of the study period. Thus, as opposed to other pharmacy refill metrics, the PDC accounts for non-persistence with medications by tracking medications during the study period despite early discontinuation. We will count the days the patient was covered by each of their prescribed antihypertensive medications based on the prescription fill date and days of supply. If prescription fills for the same medication overlap, then we will adjust the prescription start date to be the day after the previous fill has ended. Patients will be considered adherent if

they fill $\geq 80\%$ of their antihypertensive medications over the 12 months. In addition, we will assess the extent of medication non-adherence and the associated reasons based on the survey developed by [name].

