Implementation climate will be assessed with the Implementation Climate Scale (ICS) that measures shared perceptions of the policies, practices, procedures, and behaviors that are expected, supported, and rewarded to facilitate effective EBP implementation ($\alpha=.91$). The six subscales of EBP Implementation Climate are: Focus on EBP ($\alpha=.91$), Educational Support for EBP ($\alpha=.84$), Recognition for EBP ($\alpha=.88$), Rewards for EBP ($\alpha=.81$), Selection for EBP ($\alpha=.89$), and Selection for Openness ($\alpha=.91$).

Practice and participant characteristics

Practice characteristics: At baseline, we will collect data on the number of full-time equivalent staff, insurance payer mix, clinic volume, practice structure, patient demographics, staff composition (e.g., number of nurses, MAs), use of health information technology, current quality improvement initiatives, and other current or planned programs at each practice. We will also collect EHR data on the number and type of providers seen by patients enrolled in ALTA and provider turnover rate (i.e., stopped having patient encounters on the site for at least 12 months).

Clinical and nonclinical Staff characteristics: At baseline, we will collect data on education level, race/ethnicity, age, sex, primary language spoken, time working at the practice, patient load, previous trainings in chronic disease management, patient-centered communication and quality improvement methods, and job satisfaction and stress.

Patient sociodemographic and clinical characteristics: At baseline, we will collect sociodemographic data such as patient age, sex, place of birth, acculturation, primary and preferred language, insurance status, duration of HTN, number and classes of prescribed HTN medications, doses and frequencies of ingestion, and medical comorbidity. At 12 months, we will collect data on changes in doses of HTN medications, frequency of clinic visits, and the use of other medications that affect BP (e.g., NSAIDS, hormone replacement therapy).

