Following the NIH Best Practices for mixed methods research, we will construct a joint display that integrates the qualitative themes with the quantitative data to create a composite measure of implementation fidelity based on the five dimensions outlined above. Should the data be divergent, we will assign higher credence to the qualitative data because it provides richer explanation about participants' behaviors. We will also explore the association between implementation fidelity and the clinical outcomes. This analysis will be accomplished with a multilevel MANOVA (unstructured covariance matrix across two time points: baseline and 12 months). The analysis will have one within person factor — Time (baseline and 12-month coded naturally as months (0 and 12)) and one primary between-

patient factor (Randomization Group dummy coded as 0 = UC and 1 = PF). We will use the composite measure of implementation fidelity to predict changes in BP control and medication adherence at 12 months. We will use a 3-level analytic model to accounting for nesting in the data (observations nested within subjects nested within practices). Multilevel modeling software (SAS, Version 9, PROC MIXED) will be used to compute full information maximum likelihood (FIML) estimates of the model parameters. The PROC MIXED procedure will use an error structure that allows for the possibility of group differences in (a) the error variances at 12 months; and (b) the serial correlations of the baseline with the 12 month outcomes. The primary test is the treatment X time interaction, and the resulting F-test will provide the primary "intent to treat" test of the hypothesis. If this is statistically significant at the two tailed $\alpha=.05$ level, for ease of interpretation, we will estimate and report the magnitude of the treatment effect, with 95% CI for fidelity. Covariates will be included as necessary in adjusted analyses. All tests will be 2-sided, 0.05 level tests.

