6.4.3.2 Secondary Objectives Analyses

The effect of PF on BP Control

Our main clinical outcome is the proportion of patients with adequate BP control (<140/90 mmHg) at 12 months in the implementation vs. UC phase. BP control will be treated as a dichotomous outcome variable in this analysis; any patients with missing follow-up BP data will be assumed to have inadequate BP control. To examine the difference in BP control rates between the implementation and UC phases, we will utilize a generalized linear mixed model (GLMM) to assess the PF effect. A Poisson regression model will be used to predict BP control specifying a fixed effect for time, a fixed effect for treatment and a time by treatment interaction. Random effects will be specified for person and practice to account for the clustered nature of the dataset (observations within person and people within practices). As a sensitivity analysis, we will also assess an alternate definition of BP control (< 130/80 mmHg) indicated by the new hypertension guidelines. In exploratory analyses, will examine the intervention effect on BP reduction at 12 months, treated as a continuous variable. An additional sensitivity analysis will be conducted using GLMM to evaluate the effect of PF on BP reduction. We will test the treatment X time interactions in a random effects linear regression model to determine the time-specific differences BP reduction attributable to PF at the end of the implementation phase.

Randomization of the stepped-wedge design should obviate the need for adjustment, but in the case of imbalanced in baseline covariates; these will be included as necessary in adjusted analyses. All tests will be two-sided with $\alpha=0.05$ for comparison between the implementation and UC phases. Maximum likelihood estimation of mixed-effects models will be used to account for missing data; in the context of a mixed-effects model, this is equivalent to an assumption of data that are missing at random (MAR); we will conduct sensitivity analyses assessing this assumption. We will also compare participants with and without missing values with respect to baseline and practice characteristics. If differential patterns emerge, we will consider the use of multiple imputation and/or inverse probability weighting to adjust for missing data. Analyses will be conducted using Stata, SAS, and R.

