6.4.3.3. Tertiary Outcomes

We will use Generalized Linear Mixed Model to analyze the effect of ALTA on differences in relationship commitment (primary outcome) and patient-provider trust (secondary outcome). A Poisson regression model will be used specifying a fixed effect for time, a fixed effect for treatment, a time by treatment interaction, and a control group indicator. Only patients that declined participation in ALTA for the entire evaluation period will be included in the control group for the final analyses. Patients that crossover from the control group to intervention group and continue to participate in the evaluation will be counted towards the intervention group sample. Since they are asked the same questions, it does not impact the analyses. Random effects will be specified for person and clinic to account for the clustered nature of the dataset (observations within person and people within clinics). Relationship commitment will be defined as a continuous variable while patient-provider trust will be categorized as ordinal. Randomization of the stepped wedge design should obviate the need for adjustment, but in the case of imbalance in baseline covariates, these will be included as necessary in adjusted analyses. Sex will be accounted for as a covariate and examined as a potential moderator. All tests will be two-sided with $\alpha=0.05$ for comparison between the ALTA and UC phases.

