6.4.4 Subsets and Covariates

Not applicable

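### Covariates for BP control and PDC enter only on an undefined imbalance trigger; a short prespecified list of baseline values already collected would gain precision and remove discretion

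*Combined protocol and SAP*

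**What the plan says.** Section 6.4.3.2, on BP control, states: "Randomization of the stepped-wedge design should obviate the need for adjustment, but in the case of imbalanced in baseline covariates; these will be included". The model there has fixed effects for time, treatment and their interaction, with random effects for person and practice. PDC is to be analysed with similar models. The section names no covariate for either model. It does not say what counts as imbalance, between which groups it would be judged, or whether the adjusted or the unadjusted result would then lead.

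Section 6.4.3.3 repeats the premise for the tertiary outcomes ("Randomization of the stepped wedge design should obviate the need for adjustment") with the same condition, but adds: "Sex will be accounted for as a covariate and examined as a potential moderator". Section 6.4.3.1 says only "Covariates will be included as necessary in adjusted analyses", with no imbalance condition. The section headed "6.4.4 Subsets and Covariates" is marked as not applicable.

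The candidate variables are already collected. Section 6.1.4 says "At baseline, we will collect sociodemographic data such as patient age, sex, place of birth, acculturation, primary and preferred language, insurance status", and the same sentence goes on to hypertension duration, medications and comorbidity. Section 5.2.2 takes BP as the "mean of the last two measurements recorded in the EHR during each of the pre-intervention and post-intervention study periods", so continuous baseline SBP and DBP are in hand. Table 2 lists PDC at baseline and 12 months.

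**The concern.** Randomisation makes an unadjusted comparison valid on average. It does not make adjustment pointless, for three reasons.

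- **Few randomised units.** Only the order in which about 10 practices start is randomised, so chance balance on any given characteristic is weakly protected.
- **Precision.** A prognostic baseline variable reduces residual variance whether or not it is balanced. A rule that adjusts only after imbalance is seen gives up most of that gain.
- **Discretion.** With no list and no definition of imbalance, the fitted model depends on what is seen in the data and on who judges it.

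The baseline values that matter most are used only as an earlier observation of the outcome. For BP control that observation carries little information: section 5.3.2 requires uncontrolled BP at entry, so nearly every patient has the same binary baseline value. Continuous SBP still varies among these patients, but the BP control model does not use it.

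At stake are the precision of the BP control and PDC results and the assurance that their models were fixed in advance.

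**Working it through.** **1. The plan's own power figure.** Section 6.4.2 claims at least 80% power for a 15-point difference and over 90% for 20 points, with 10 sites, 700 patients and ICC 0.01 to 0.05. The layout is not given. I assumed five sequences of two practices (Figure 1 shows five cohorts; the text of 5.1 has four waves of two), six periods, a usual-care rate of 29% (prior trial, 6.4.2), two-sided 0.05, and one observation per patient, so m = 700/60 = 11.67 per practice-period.

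Hussey-Hughes variance: I·s²(s² + Tτ²) / [(IU − W)s² + (U² + ITU − TW − IV)τ²], with I = 10, T = 6, U = 30, W = 220, V = 110.

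- Total variance, averaged over phases: (0.29×0.71 + 0.44×0.56)/2 = 0.2262.
- ICC 0.01: τ² = 0.00226, s² = 0.01919, SE = 0.0538; power = Φ(0.15/0.0538 − 1.96) = 79.6%.
- ICC 0.05: τ² = 0.01131, s² = 0.01842, SE = 0.0585; power = 72.7%.
- 20 points: 95.9% and 92.6%.
- Two observations per patient (1,400), 15 points: 96.5% and 94.0%.

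The 20-point claim is met. The 15-point claim is met or not depending on the unstated layout, so it is neither confirmed nor refuted.

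**2. Continuous SBP (exploratory in the plan).** The documents give no correlation ρ between baseline and 12-month values, so ρ is assumed. If the planned time-by-treatment test is read as a difference in change, with equal variances and no practice clustering:

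- change score: variance proportional to 2σ²(1 − ρ);
- baseline as covariate: variance proportional to σ²(1 − ρ²);
- SE ratio: √[(1 − ρ²)/(2(1 − ρ))] = √[(1 + ρ)/2].

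| ρ | SE ratio | Reduction in SE |
|---|---|---|
| 0.3 | √0.65 = 0.806 | 19% |
| 0.5 | √0.75 = 0.866 | 13% |
| 0.6 | √0.80 = 0.894 | 11% |

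**3. Binary BP control.** Simulation with 10 practices, 6 periods, 12 patients per practice-period, ICC 0.03, and 3,000 runs per setting, analysed by generalised least squares on the risk-difference scale. The log odds ratio was 0.654 = ln(0.44/0.56) − ln(0.29/0.71). The trigger was assumed to be p < 0.05 on one covariate, since the plan gives none.

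| Covariate (log-odds per SD) | Never adjust | Adjust if imbalanced | Always adjust |
|---|---|---|---|
| 0.5 (moderate) | 70.4% | 70.7% | 72.1% |
| 1.0 (strong) | 58.3% | 59.0% | 65.7% |

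The trigger fired in about 5% of trials. It kept 0.3 of 1.7 points (18%) of the available gain in the first row and 0.7 of 7.4 points (9%) in the second. Type I error was 4.1% to 4.8% for all three strategies. The rows should not be compared with each other: at the same log odds ratio the mean risk difference was 0.142 in the first and 0.124 in the second. The Monte Carlo standard error of one power estimate is about √(0.7×0.3/3000) = 0.8 point.

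**4. Against the layout in step 1.** Multiplying the individual-level variance by (1 − R²), with R² assumed, gives power for 15 points at ICC 0.01 / 0.05 of 79.6% / 72.7% at R² = 0, 83.1% / 76.7% at 0.10, and 86.7% / 80.9% at 0.20.

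**The case against.** The strongest reply is that baseline is already in the models, as a repeated outcome with a person effect, and that the loss is small. The first part is right. It is why the SBP comparison above is made against a change score. Set against an unadjusted follow-up-only analysis, which is not planned, √(1 − ρ²) would give reductions of 5%, 13% and 20%. The reply does not dispose of the point, because an unconstrained baseline response is less efficient than baseline adjustment, and binary baseline control is nearly constant. The second part also stands for a moderate covariate: about two points of power.

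A reader might infer more than the documents support:

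- **That the whole plan adjusts only on imbalance.** Sex is prespecified for the tertiary outcomes, 6.4.3.1 has no imbalance condition, and the path model in 6.4.3.2 includes practice, staff and patient variables regardless of balance.
- **That the BP and PDC contrasts compare different patients by phase and are confounded by case mix.** Section 6.1.1 recruits patients and takes baseline measures during usual care, and the models treat observations as repeated within person. If the same patients supply both phases, stable characteristics largely cancel. A case-mix difference is possible but not shown. Adjusting for age or sex would not cure a calendar-time effect, for which the model already has a time term.
- **That the rule inflates false positives.** The simulation shows no inflation.
- **That imbalance will probably be declared by chance.** Ten independent tests at 5% would flag at least one variable with probability 1 − 0.95^10 = 40%, but the plan specifies neither significance tests nor ten variables. Section 6.4.3.5 describes descriptive summaries.

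**Conclusion.** The point holds as one of precision and analyst discretion in secondary and tertiary analyses, not of bias or type I error. The stated reason for not adjusting is insufficient, and the trigger gives up most of the available gain: in the simulation it kept less than a fifth.

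The size is modest to moderate and rests on assumptions: an 11% to 19% smaller standard error for SBP over ρ from 0.6 down to 0.3, and about 2 to 7 points of power for binary BP control over the two covariate strengths tried. The SBP figures also assume equal variances, which the entry requirement for uncontrolled BP may disturb. The simulation is of single observations per patient and does not include the person-level repeated measures. For PDC no figure is offered; entry below 80% adherence restricts its baseline range and may reduce the gain.

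**What to change.** - Delete the imbalance condition in 6.4.3.2 and 6.4.3.3.
- In 6.4.4, prespecify a short list of patient-level covariates already collected, for example age and sex, plus continuous baseline SBP for BP control and baseline PDC for PDC. Make that the main analysis whatever the observed balance, and report the unadjusted result as a sensitivity analysis. With about 10 practices, avoid a long list of practice-level terms.
- State how each baseline value is used: either as a covariate in a model of the follow-up outcome, or as a response with baseline means constrained equal. Simply adding it to the planned repeated-measures model would put it on both sides.

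The cost is a minor re-specification of the models, somewhat more than a change of wording, with no new data collection. It should be settled before outcome data are examined.

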- Being deemed unable to comply with the study protocol (either self-selected or by indicating during screening that s/he could not complete all requested tasks)
- Participation in other hypertension-related clinical trials
- Have significant psychiatric comorbidity or reports of substance abuse (as documented in the EHR)
- Plan to discontinue care at the practice within the next 15 months

Clinic and nonclinical staff Eligibility Criteria

Inclusion criteria:

- Primary care provider (MD/DO, NP), Nurse, Medical Assistant, or administrative staff employed at the participating practices and interacts with at least five patients with a diagnosis of hypertension.

Exclusion criteria:

- Refuse to participate.

Number of Participants

Implementation Phase

Clinical and nonclinical staff:

Surveys and interviews: 204

Patients:

Surveys: Randomly selected sample of 70 patients from each of the 10 participating primary care clinics (n=700). We will also be selecting a sample of 300 patients across participating clinics who met the eligibility criteria but did not participate in ALTA to participate as a control group.

Interviews: A randomly selected subsample of 30 patients with uncontrolled HTN who participated in ALTA (n=700)

Table of Contents

1 – Introduction	9
1.1 Introductory Statement	9
2 – Background	10
2.1 Background/prevalence of research topic	10
3 – Rationale/Significance	11
3.1 Problem Statement	11
3.2 Purpose of Study/Potential Impact	11
3.3.1 Potential Benefits	12
3.3.2 Potential Risks	13
4 – Study Objectives	15
4.1 Hypothesis	15
4.2 Primary Objective	15
4.3 Secondary Objectives (if applicable)	15
5 – Study Design	16
5.1 General Design	16
5.1.1 Study Duration (if applicable)	17
5.1.2 Number of Study Sites	17
5.2.1 Primary Outcome Variables	17
5.2.2 Secondary and Exploratory Outcome Variables (if applicable)	17
5.3 Study Population	19
5.3.1 Number of Participants	19
5.3.2 Eligibility Criteria/Vulnerable Populations	20
6 – Methods	22
6.1 Description of PF implementation strategy	22
6.1.1 Usual Care (UC) Phase	22
6.1.2 Pre-implementation phase	22
6.1.3 Description of Implementation phase	23
6.1.4 Selection of Instruments/Outcome Measures	24
6.1.5 Intervention Administration	31
6.1.6 Reaction Management	32

6.2.1 Efficacy	32
6.2.2 Safety/Pregnancy-related policy	33
6.2.2.1 Adverse Events Definition and Reporting	33
6.2.3 Pharmacokinetics (if applicable)	33
6.2.4 Biomarkers (if applicable)	33
6.3.1 Study Schedule	33
6.3.2 Informed Consent	34

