6.4.2 Sample Size Considerations

Power calculations are based on the clinical outcome of BP control using our prior work implementing the ALTA model in a community-based clinic. In the former trial, we found a significant improvement in attainment of BP control at 6 months among patients randomized to the intervention group compared to the UC group (51% vs. 29%, $p=.03$). We expect a similar group difference of a 20% increase in BP control between the implementation and UC phases in the current study. Calculations of achieved power were estimated with a stepped-wedge design using Power Analysis and Sample Size (PASS) software program. The power calculations show that we can recruit 10 sites and 700 patients and have at least 80% power to detect a more conservative 15% difference in BP control between the UC and implementation phases for intraclass correlation coefficients (ICCs) ranging from 0.01 to 0.05. Using our original estimate of a 20% difference in BP control, we would have over 90% power to detect a difference between the UC and implementation phases with 10 sites and 700 patients.

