Associations between rates of BP control and implementation fidelity will be evaluated using structural equation modeling methods. We will estimate a path model using maximum likelihood estimation to investigate relationships between BP control and implementation fidelity. Implementation fidelity will be identified as individual and simultaneous predictors of BP control. Practice-, staff-, and patient-level variables, which may influence level of implementation fidelity, will also be included in the model. In addition to the direct effects of each variable, the indirect effects from each variable to BP control via mediator variables will be estimated as the product of component direct effects and tested using bootstrapped 95% confidence intervals. Structural equation modeling analyses will be conducted using R and fit indices will be evaluated to ensure model fit.

The effect of PF on medication adherence

We will estimate similar models as BP control with PDC, calculated from available pharmacy records, as the outcome. A GLMM model using maximum likelihood estimation will be utilized to estimate the effect of PF on medication adherence with fixed effects specified for treatment phase, time, and the treatment by time interaction. We will apply any necessary transformations to the PDC outcome to improve the approximation to normality, and explore alternative regression strategies, such as rank regression and/or beta regression.

The effect of practice and individual-level moderators on implementation fidelity of ALTA

Using validated surveys (described above), we will explore potential practice-, staff- and patient-level moderators, assessing interactions between the PF strategy, level of implementation fidelity and modifiers. Potential moderators of the association between PF and implementation fidelity of ALTA will be evaluated using structural equation modeling methods. We will determine potential moderators by examining the PF x moderator interaction effects. Fit indices will be evaluated for all models to ensure adequate model fit.

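### The path model relating fidelity to BP control does not say how practice clustering is handled; with patients treated as independent, its direct path would give about 13–35% false positives instead of 5%

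*Combined protocol and SAP*

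**What the plan says.** Section 6.4.3.2 plans two structural equation analyses.

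- **Fidelity and BP control.** "We will estimate a path model using maximum likelihood estimation to investigate relationships between BP control and implementation fidelity". Fidelity predicts BP control, entered both singly and jointly. Variables measured on practices, staff and patients go into the same model. Indirect effects are to be "tested using bootstrapped 95% confidence intervals".
- **Moderators of fidelity.** "Potential moderators of the association between PF and implementation fidelity of ALTA will be evaluated using structural equation modeling methods". This paragraph names interaction terms and fit indices, but neither maximum likelihood nor a bootstrap.

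Neither paragraph mentions a practice random effect, a multilevel SEM, cluster-robust errors or the unit to be resampled. Other analyses do state the nesting. Section 6.4.3.1 uses the composite fidelity measure to predict change in BP control and adherence, and says: "We will use a 3-level analytic model to accounting for nesting in the data". The BP-control model in 6.4.3.2 has random effects for person and practice, and the tertiary models in 6.4.3.3 have them for person and clinic. Section 6.4.2 sizes the trial for "intraclass correlation coefficients (ICCs) ranging from 0.01 to 0.05".

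**The concern.** Section 6.4.3.1 scores most of fidelity by practice. Adherence is the share of components a practice fully implemented. Average dose is coaching sessions over clinic encounters. Responsiveness is averaged within practice, and differentiation is overlap with other initiatives at the site. Only the audiotaped coaching score, on a 10% sample of sessions, is clearly recorded below practice level.

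Attached to patients, such a score takes about 10 distinct values repeated over 700 rows. A patient-level likelihood or a bootstrap of patients then counts 700 pieces of information where there are about 10. Intervals come out too narrow, and chance differences between practices can be reported as an effect of fidelity. The plan would also hold two analyses of one question, one with practice nesting and one without it stated, and no rule for which prevails.

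**Working it through.** The documents give no error rate for these models, so there is no figure of the plan's own to reproduce. The power figure in 6.4.2 concerns the phase comparison and does not bear on this point.

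**Inputs**
- Practices and patients: "we can recruit 10 sites and 700 patients" (6.4.2), that is 70 per practice, as in the synopsis and 5.3.1. Section 6.3.4 also speaks of recruiting about 500, that is 50 per practice.
- ICC for BP control: 0.01 to 0.05 (6.4.2).
- Nominal level: 5% two-sided, as for the phase comparison in 6.4.3.2. The SEM paragraphs state none, but a 95% interval implies the same level.
- Assumptions: one fidelity value per practice, one BP-control result per patient, and no true association.

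**Formula.** For a predictor constant within practice, the variance of its coefficient is understated by DE = 1 + (m − 1) × ICC. The actual false-positive rate is 2 × [1 − Φ(1.96/√DE)].

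- ICC 0.01, m = 70: DE = 1 + 69 × 0.01 = 1.69; 1.96/√1.69 = 1.508; rate 13.2%.
- ICC 0.05, m = 70: DE = 1 + 69 × 0.05 = 4.45; 1.96/√4.45 = 0.929; rate 35.3%.

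| ICC | DE, m = 70 | Rate, m = 70 | DE, m = 50 | Rate, m = 50 |
|---|---|---|---|---|
| 0.01 | 1.69 | 13.2% | 1.49 | 10.8% |
| 0.02 | 2.38 | 20.4% | 1.98 | 16.4% |
| 0.03 | 3.07 | 26.3% | 2.47 | 21.2% |
| 0.05 | 4.45 | 35.3% | 3.45 | 29.1% |

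**Simulation, 10 practices of 70.** A patient-level maximum-likelihood test rejected in about 12–13% of 10,000 null trials at ICC 0.01 and 35–36% at ICC 0.05. A percentile bootstrap of patients (4,000 trials) gave 14.5% and 36.7%, so bootstrapping patients does not help. A test on the 10 practice means with 8 df (10 practices less 2 parameters) gave about 4.5–5.5% throughout.

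**If fidelity varies partly within practice.** Then DE = 1 + (m − 1) × ICC of fidelity × ICC of BP control. The documents do not give the first ICC, so these values are assumed, with m = 70:
- Fidelity ICC 0.5: DE 1.345 to 2.725, rate about 9% to 24%.
- Fidelity ICC 0.2: DE 1.138 to 1.69, rate about 7% to 13%.

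**Moderator model.** The layout is not stated, so I assumed one fidelity value per practice copied to 20 staff (204/10) or to 70 patients, and simulated the plain association, not the interaction with PF.

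| ICC of moderator (assumed) | 20 per practice | 70 per practice |
|---|---|---|
| 0 | about 6% | about 5% |
| 0.05 | 16% | 36% |
| 0.2 | 39% | 62% |
| 1 (constant within practice) | 69% | 85% |

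**The case against.** The best defence is that the plan is silent and has not chosen wrongly. Maximum likelihood does not imply independence: 6.4.3.1 uses full-information maximum likelihood for its 3-level model. The resampling unit is left open, and the authors model nesting everywhere else. This stands in part. A reader might infer that the plan has decided to ignore clustering and that its error rates are 13–35%. The documents support only the conditional: that is what the rates would be if the model were fitted as worded, with patients independent. An analysis plan should still settle this, and nothing in the paragraph points to an adjustment.

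It is also fair that one fidelity value per practice is an inference. The composite's level is never stated, coaching quality is scored by session, and responsiveness starts from individual surveys. It is the natural reading of 6.4.3.1, but the partly-within-practice figures belong beside the main range.

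Other stronger readings are tempting and not supported:
- **The same range for moderators.** Neither the estimator nor the bootstrap is named there, and the rate runs from about 5% to 85% with the clustering of the moderator.
- **A much larger error for five domains entered together.** Simulation gave at least one false positive in 45–84% of trials, but five independent valid tests already give 1 − 0.95⁵ = 23%. Those figures mix multiplicity with clustering, and the paragraph does not say that the five domains are the predictors.
- **A threat to the trial's main clinical result, or a causal claim.** The PF effect on BP control is tested with a practice random effect, and the SEM text speaks of associations.

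**Conclusion.** The gap is real and should be closed. The path model of fidelity on BP control names neither a practice level nor a resampling unit, while the same association is nested by practice in 6.4.3.1. Treating patients as independent would give a false-positive rate for the direct path of about 13% (ICC 0.01) to 35% (ICC 0.05) with 70 patients per practice, or about 11% to 29% with 50. This rests on fidelity being constant within practice and on the plan's own ICCs, and the rate falls if fidelity varies within practice. The moderator model shares the gap, but no single figure describes it. These are secondary or exploratory analyses, so this is a correction to make before analysis and not a flaw in the trial's design.

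**What to change.** In 6.4.3.2:

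1. Account for practice in every path that involves fidelity. Either extend the 3-level model of 6.4.3.1 with fidelity at practice level, or regress practice-level BP control on fidelity. Use small-sample t inference, with 8 df for a single fidelity score.
2. Bootstrap by resampling whole practices.
3. State that only 10 practices inform any fidelity effect, and present the joint multi-domain and indirect-effect results as descriptive.
4. For moderators, use practice means for practice-level constructs. Keep staff-level moderators in a model with a practice random effect, so that the individual-level question in 4.3 is not lost. That model is informative only for fidelity measures that vary within practice, such as the coaching-session score. Because staff surveys are anonymous (6.3.2), the plan should say whether the two can be linked.
5. State that the nested analysis in 6.4.3.1 prevails if the two disagree.

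The cost is wider intervals and some results becoming descriptive. Only the analysis wording changes; the fidelity-to-BP correction needs no new data.
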